NCT 02749045

Date: 5/2016

Title: The Simultaneous Assessment of Invasive Fractional Flow Reserve and SPECT Myocardial Ischemia Using Regadenoson in the Catheterization Laboratory.

[name] [name]; [name] (Nuclear Cardiology)
[name]; [name] (Intervention Cardiology)

Background: Coronary revascularization guided by either invasive Fractional Flow Reserve (FFR) measurement or the presence and extent of myocardial ischemia on stress testing is associated with better outcome compared to coronary anatomy-based revascularization(1). The appropriate use criteria (AUC) increasingly emphasize the importance of establishing the functional significance of coronary lesions prior to percutaneous coronary interventions (PCI)(2). Myocardial ischemia is most often assessed by myocardial perfusion stress- single-photon emission computed tomography (MPS). However, FFR and MPS-derived ischemia measures do not always correlate, and disparities are known to exist in as many as 40% of cases (3). While the complex interplay between focal epicardial disease, diffuse epicardial disease and microvascular disease is the physiological basis for these disparities, technical factors including temporal and protocol differences between FFR estimation and ischemia estimation may also play a role. Initial validation studies found high correlation between stenosis with FFR <0.65 and myocardial ischemia in single vessel disease, while the contemporary practice is to attribute hemodynamic significance to FFR <0.80 (4,5). Furthermore these original studies were performed using dipyridamole or adenosine stress, which have different hyperemic flow profiles compared to regadenoson (6). This study aims to determine the correlation between simultaneous FFR and MPS obtained using regadenoson in the catheterization laboratory. The protocol is designed to eliminate temporal and stress protocol differences between FFR and MPS. Our group has previously validated the use of regadenoson for FFR estimation (7).

Aims:

1. To determine the correlation between FFR and ischemia (presence and extent) assessed simultaneously in the catheterization laboratory using regadenoson.
2. To determine the optimal cut off of FFR with regadenoson stress that predicts the presence of myocardial ischemia on MPS

Methodology:

Study Population:

Inclusion criteria:

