Patients will be monitored for 2-6 hours, or overnight, as clinically indicated following diagnostic coronary angiography and PCI, respectively.

A low dose resting MPS will be performed the next day, if the stress MPS is abnormal.

SPECT Analysis:

Perfusion image analysis will be performed using a standard 17 segment model and polar plots. Quantitative perfusion defect analysis using the QGS (Cedars-Sinai Medical Center, CA) will be used to determine the Total Perfusion Defect size, which will be the parameter used for analysis. Image interpretation will be performed by physicians blinded to the results of FFR testing.

Statistical Analysis:

Standard statistical tests to correlate FFR with the presence and extent of MPS will be applied to patients groups with concordant and discordant FFR/SPECT studies. The percentage of patients with concordant FFR and SPECT results will be determined. The characteristics of patients with discordant FFR and SPECT results will be described (mean FFR and range of FFRs, single vs. two- vessel disease, lesion characteristics such as diffuse vs. discrete disease). An ROC curve analysis will be performed to define the cut-off of FFR that optimally predicts SPECT ischemia.

Adverse event monitoring:

All study procedures are clinically indicated except the Tc-99m injection and SPECT acquisition, which are clinically approved procedures. Any adverse events will be reported.

References

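### The extent half of Aim 1 has no stated all-patient analysis, and the only correlation sentence points to groups defined by the same two variables

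*Combined protocol and SAP*

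**What the plan says.** Aims, item 1, is "To determine the correlation between FFR and ischemia (presence and extent) assessed simultaneously in the catheterization laboratory using regadenoson". The Background states the same purpose, also without a subgroup: "This study aims to determine the correlation between simultaneous FFR and MPS obtained using regadenoson in the catheterization laboratory".

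The SPECT Analysis section names the extent measure: "Total Perfusion Defect size, which will be the parameter used for analysis".

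The Statistical Analysis section has one sentence on correlation. It says that unnamed standard tests to "correlate FFR with the presence and extent of MPS will be applied to patients groups with concordant and discordant FFR/SPECT studies". Three other analyses follow:

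- agreement: "The percentage of patients with concordant FFR and SPECT results will be determined";
- a description of the discordant patients;
- the cut-off: "An ROC curve analysis will be performed to define the cut-off of FFR that optimally predicts SPECT ischemia".

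None of these three relates FFR to extent in all patients.

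**The concern.** A patient is concordant or discordant because of the FFR result and the SPECT result, which are the two variables to be correlated. Splitting on agreement keeps concordant patients in the two quadrants where low FFR goes with a positive scan and high FFR with a negative one. Discordant patients occupy the other two quadrants. A correlation inside either group is therefore partly produced by the split.

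An analyst could follow the sentence as written and report one correlation per group. The concordant figure would overstate the FFR-extent relationship, most of all where the true relationship is weak. The discordant figure would be pushed towards a positive value. Neither answers Aim 1, and nothing else in the plan supplies the extent result.

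**Working it through.** **Plan's own figure.** There is none to reproduce. The sample size of 50 is a recruitment yield (50/500 = 10% of those screened), with no target correlation or precision.

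**What each planned analysis covers**

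| Analysis | Patients | Presence | Extent |
|---|---|---|---|
| Correlation sentence | the two groups; separate or pooled not stated | yes | yes |
| Percentage concordant | all | yes | no |
| Description of discordant patients | discordant only | no | no |
| ROC curve | all | yes | no |

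Only the first row reaches extent, and its analysis set is open.

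**Inputs for the size of the problem**

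- From the Background: "disparities are known to exist in as many as 40% of cases". Here it serves as a ceiling on plausible discordance.
- Assumed, because the plan gives none of these: bivariate-normal FFR and extent; one FFR cut-off; one classification per patient; true Pearson r of 0, -0.3, -0.5, -0.7 or -0.8; and nine pairs of FFR-positive/SPECT-positive percentages (50/50, 50/40, 50/30, 50/20, 40/40, 40/30, 40/20, 30/30, 30/20).

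**One case by hand: true r = 0, pair 30/20.** Let x be FFR (positive = low) and y be extent (positive = high), both standardised. The normal density is 0.3477 at the 30% cut and 0.2800 at the 20% cut.

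- Concordant share = 0.3 × 0.2 + 0.7 × 0.8 = 0.62, so 38% are discordant.
- Mean of xy = -2 × 0.3477 × 0.2800 / 0.62 = -0.3140.
- Mean of x = (0.8 - 0.2) × 0.3477 / 0.62 = 0.3365. Mean of y = (0.3 - 0.7) × 0.2800 / 0.62 = -0.1806.
- Covariance = -0.3140 + 0.3365 × 0.1806 = -0.2532.
- Mean of x² = (0.2 × 0.4823 + 0.8 × 0.5177) / 0.62 = 0.8236, where 0.4823 = 0.3 + 0.5244 × 0.3477. The variance of x is 0.8236 - 0.3365² = 0.7103.
- Mean of y² = (0.3 × 0.4356 + 0.7 × 0.5644) / 0.62 = 0.8480, where 0.4356 = 0.2 + 0.8416 × 0.2800. The variance of y is 0.8480 - 0.1806² = 0.8154.
- Concordant r = -0.2532 / √(0.7103 × 0.8154) = **-0.33**, although the true correlation is zero.

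**All scenarios by simulation** (4,000,000 draws each; a rerun with 2,000,000 agreed to within about 0.01). Only pairs with at most 40% discordance are shown.

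| True r | Pairs kept | % discordant | Concordant r | Discordant r | Concordant too negative by |
|---|---|---|---|---|---|
| 0 | 1 (30/20) | 38 | -0.33 | +0.63 | 0.33 |
| -0.3 | 5 | 32–39 | -0.53 to -0.67 | +0.47 to +0.59 | 0.23–0.37 |
| -0.5 | 9 | 27–39 | -0.65 to -0.76 | +0.21 to +0.56 | 0.15–0.26 |
| -0.7 | 9 | 21–34 | -0.78 to -0.83 | -0.02 to +0.53 | 0.08–0.13 |
| -0.8 | 9 | 18–32 | -0.84 to -0.87 | -0.19 to +0.52 | 0.04–0.07 |

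The discordant sign fails to reverse at 50/20 when r is -0.7 (-0.02) or -0.8 (-0.19).

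**Pooled precision for comparison.** For a Spearman correlation of -0.5 in 50 patients, the standard error on the Fisher z scale is √((1 + 0.5²/2)/47) = 0.155. The 95% CI is tanh(-0.549 ± 1.96 × 0.155), or about -0.69 to -0.24.

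**Zero-extent check.** Suppose every SPECT-negative patient has extent 0. At true r = -0.3 (the same five pairs, n = 50), the mean Spearman correlation is -0.57 to -0.78 in concordant patients and +0.69 to +0.77 in discordant patients. The pattern does not depend on extent being normally distributed.

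**The case against.** The strongest reply is that the plan never says the correlations are computed separately. The two groups together make up every classifiable patient, and the Aims and Background name no subgroup, so a pooled analysis fits. The same sentence also covers presence. With a single FFR cut-off, the two dichotomised results agree in every concordant patient and in no discordant patient by definition, so a within-group analysis of presence would be empty. That favours a pooled analysis or a comparison between the groups.

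This stands as far as it goes. A reader might infer that the plan prescribes within-group correlations, or that Aim 1 has no whole-cohort analysis at all. The documents support neither: the wording is open, and presence has two all-patient analyses. But a pooled extent analysis is not stated, the coefficient is not named, and a between-group comparison would not give the FFR-extent correlation either.

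A second reply concerns size. The scenarios are assumed, and at r = 0 eight of the nine pairs exceed 40% discordance. A reader might take the larger r = 0 values, up to 0.64, as the expected distortion; the Background figure does not support that. The same ceiling is therefore applied at every r above, which leaves 0.33 at r = 0. It is also fair that at -0.7 to -0.8 the concordant distortion is small beside the sampling error of 50 patients.

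**Conclusion.** The point holds as a gap in the stated analysis, with a conditional harm. The plan does not say in which patients FFR will be correlated with extent, and the only sentence on it names groups selected on both variables. If the correlation is pooled, no bias of this kind arises. If it is computed within groups, the concordant figure is too negative by 0.33 at a true r of 0, 0.23–0.37 at -0.3 and 0.15–0.26 at -0.5, falling to 0.04–0.13 at -0.7 to -0.8. The discordant figure is often, but not always, reversed in sign.

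These sizes rest on bivariate normality, the nine assumed positivity pairs and the Background's 40% as a ceiling. The direction follows from the selection itself. The point should be fixed before analysis; confidence is medium because the intended reading is unknown.

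**What to change.** Replace the correlation sentence with:

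> The correlation between FFR (of the vessel tested at tracer injection) and Total Perfusion Defect size will be estimated in all patients with both measurements, using a rank correlation with 95% CI, as the Aim 1 extent analysis.

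Use the concordant/discordant split only for the concordance percentage and the description of patients. Nothing need be added for presence. The vessel is specified because, where two vessels are tested, the Study Design section ties the tracer injection to the one judged more severe. Two definitions remain to be stated elsewhere: the cut-offs that make a result concordant, and whether defect size is the stress value or the stress-rest difference.

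The cost is one sentence, with no extra patients or data. The reported figure may be less favourable than a concordant-group one. Ties will also weaken a rank correlation if many patients have zero extent. With 20–50% SPECT-positive under the zero-extent model, Spearman falls from about -0.29 to between -0.21 and -0.26 at a true r of -0.3, and from -0.68 to between -0.49 and -0.63 at -0.7. The report should therefore give the number of patients with zero extent.
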